1. STUDY SCHEDULE OF EVENTS

Study Phase	Screening		Treatment (Week 1 to Week 52)					Phase 2 Follow-up	Phase 3 follow-up (ongoing AEs at end of Phase 2)		
Week	-6 Weeks to Day -1		Week 1, Day 1	Week 4 ±3 days	Week 12 ±2 weeks	Week 24 ±2 weeks	Week 52 ± 2 weeks	Week 64 ±2 weeks (EOS)	Week 76 ± 2 weeks	Week 89 ± 2 weeks	Week 104 ± 2 weeks
Visit Number	1a/ 1b ^a		2	3	4	5	6	7a/7b ^b	8	9	10
Written informed consent	X		X ^c								
Randomization			X								
Inclusion & exclusion	X		X								
Demographics	X										
Body height and weight	X										
Medical, surgical & social history	X		Update								
Prior medications ^d	X		Update								
Physical examination ^e	X		X	X	X	X	X	X			
Vital signs ^f	X		X	X	X	X	X	X			
12-lead ECG	X			X			X	X	Repeat if needed to follow AE		
Hematology/ biochemistry ^g	X		X	X	X	X	X	X	Repeat if needed to follow AE		
G6PD testing	X										
Methemoglobin (MetHb%)	X		X	X	X	X	X	X	Repeat as needed to follow AE		
Serology ^h	X										
Pregnancy test ⁱ	X		X	X	X	X	X	X			
PK blood collection for tafenoquine ^j			X	X	X	X	X				

Study Phase	Screening		Treatment (Week 1 to Week 52)					Phase 2 Follow-up		Phase 3 follow-up (ongoing AEs at end of Phase 2)		
Week	-6 Weeks to Day -1		Week 1, Day 1	Week 4 ±3 days	Week 12 ±2 weeks	Week 24 ±2 weeks	Week 52 ± 2 weeks	Week 64 ±2 weeks (EOS)		Week 76 ± 2 weeks	Week 89 ± 2 weeks	Week 104 ± 2 weeks
Visit Number	1a/ 1b ^a		2	3	4	5	6	7a/7b ^b		8	9	10
Alcohol breath test	X		X									
Urinalysis (dipstick) and urine drug screen ^k	X		X	X	X	X	X	X		Repeat urinalysis only if needed to follow AE		
Ophthalmic assessments (before dilation: BCVA (ETDRS letter score FM-100 hue test, MARS letter contrast sensitivity test, M-Chart and slit lamp examination/grading of deposits after Screening. (After dilation: SD-OCT, qFAF, digital photograph of cornea, retina (conventional and wide field), slit lamp retinal exam and IOP measurement		X			X	X	X		X	Repeat if needed to follow AE		
Microperimetry ^l		X				X	X		X	Repeat if needed to follow AE		
MINI 7.0.2	X				X	X	X	X		Repeat if needed to follow AE		
DHI			Only collected if participant reports AE of dizziness or vertigo							Repeat if needed to follow AE		
LSEQ			X	X	X	X	X	X				
C-SSRS			X	Every 4 weeks ± 1 week								
AE collection			X	X	X	X	X	X		Repeat if needed to follow AE		
Concomitant medication			X	X	X	X	X	X				
IMP administration			200 mg daily x 3 days Week 1, then 200 mg once/week through to Week 52									

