5.6. Route of Administration, Dosage Regimen, Treatment Period, and Justification

The 600 study participants will be randomized to the tafenoquine or the placebo group in a 1:1 ratio using clinical site as a randomization variable; two groups of 300 participants each will be enrolled in each group.

Each active IMP tablet will contain 100 mg tafenoquine. The dose to be administered orally is 200 mg tafenoquine (2 x 100 mg tablets) per day for three consecutive days (loading doses), followed by another 200 mg dose once per week for the following 51 weeks (beginning post-loading dose Day 10). The placebo group will receive identically-matched double-blind placebo tablets. The IMP tablets will be taken with 180 mL of water but there is no restriction on whether the tablets are taken with or without food.

Safety evaluations will include the following assessments: AE evaluation, physical examination, vital signs, laboratory parameters (hematology, biochemistry, and urinalysis). These will be performed at various time points throughout the study to assess baseline function and any changes from baseline after administration of IMP. Hematology, including methemoglobin assessment, biochemistry and urinalysis will be conducted at Screening, Weeks 4, 12, 24, 52, and 64. Clinical laboratory values indicative of an AE at EOS Week 64 will be repeated during the Follow-up Phase at Weeks 76, 89, 104 until resolution or stabilization.

Previous clinical studies support a recommended dosage tafenoquine regimen for malaria prophylaxis of a loading dose of 200 mg once daily for 3 days before travel to a malarious area, followed by weekly 200 mg maintenance doses while in the malarious area, for a period not exceeding 6 months, and an additional dose of 200 mg at one week of return from travel (60P IB).

In this study tafenoquine will be administered for 12 months to confirm the long term safety of tafenoquine past the 6-month safety window for travelers or military personnel who may be in a malarious area for prolonged periods of time.

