6.4.2. Concomitant Treatment

General concomitant medication restrictions:

- Tafenoquine may inhibit drug transporters in the kidney. Since inhibition of these transporters may lead to increased exposure to medications that they excrete, when tafenoquine is co-administered with, substrates or inhibitors of MATE or OCT2, it may be advisable to re-evaluate safety and/or efficacy of the latter drugs.
- All participants will be questioned about concomitant medication at each clinic visit. All concomitant medications taken during the study must be recorded with indication, daily dose, route of administration and start and stop dates of administration; and
- Medications taken within 28 days before the first dose of the IMP will be documented as prior medications. Medications taken after the first IMP dose will be documented as concomitant medications.

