After completion of the assessments and after administration of the tafenoquine dose, participants will be allowed to leave the Study Site if they are considered to be in good health by the investigator.

8.3. Treatment Period: Week 4, 12, 24, and 52 (Visits 3, 4, 5 and 6)

Participants will report to the Study Site in the morning.

The following assessments will be performed over the treatment period:

- Abbreviated physical examination- a symptom-directed physical examination will be performed based on signs and symptom the participant has reported verbally. A symptom-directed physical examination may also be performed if it is required according to the opinion of the investigator.
- Vital signs (blood pressure, pulse rate, respiratory rate and sublingual body temperature).
- 12-lead ECG (Week 4 and 52).
- Blood sampling for determination of the following parameters:
 - CBC;
 - Biochemistry;
 - MethHb %;
 - Plasma for PK analysis;
- Urine sampling for determination of the following parameters:
 - Urine β -HCG pregnancy test (WOCBP only) at Weeks 4, 12, 24 and 52;
 - Routine urinalysis (dipstick and urine microscopy if blood, leukocyte esterase, or nitrites are positive); and
 - Urine drug screen (amphetamines, methamphetamines, barbiturates, benzodiazepines, cocaine, methadone, opiates, phencyclidine, tetrahydrocannabinols, and tricyclic antidepressants);

Ophthalmic Assessments: The following ophthalmic tests will be performed routinely during the Treatment Period at Weeks 12, 24 and 52 Ophthalmic assessments may be scheduled as a second visit during weeks when most of the examinations are performed to not overburden the length of the visit for subjects.

Before pupil dilation:

- BCVA (ETDRS letter score);
- Color vision assessment with FM-100 hue test;
- Mars letter contrast sensitivity test;

- M-chart distortion test; and
- Slit lamp examination and corneal deposit grading (the Orlando system).

After pupil dilation:

- MAIA Microperimetry (only Weeks 24 and 52);
- Heidelberg Spectralis SD-OCT (including wide field macula scan);
- Heidelberg Spectralis qFAF (set of 3 images to ensure consistency in measurement);
- Digital photograph of corneal surface (conventional and wide field);
- Digital photograph of retina (conventional and wide field);
- Slit lamp retinal examination and IOP measurement; and
- **Psychiatric Assessments**
 - M.I.N.I. English Version 7.0.2;
 - DHI (only if a participant reports AE of dizziness or vertigo); and
 - LSEQ.

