- Recording AEs and any concomitant medications.
- Electronic compliance system, diary cards and used blister packs checked. Number of tablets taken, date and time recorded in eCRF. Diary cards and final used blister packs collected at Week 52.

Also every 4 weeks \pm 1 week during the treatment period, a C-SSRS interview will be conducted either by telephone at any time or in person at a clinic visit at the discretion of the site staff.

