9.2.9. Dizziness Handicap Inventory (DHI)

Dizziness is common symptom that is reported frequently with varying degrees of impact on the individual's quality of life. Dizziness can be caused by many different clinical conditions. While the impact of dizziness is predictive, this disorder can be more consistently evaluated by using a tool such as the DHI. The DHI is a reliable, comprehensively validated and clinically useful tool to measure self-perceived handicap associated with the symptom of dizziness from a variety of causes ([Treleaven 2005](#)).

Participants who admit to new or worsening dizziness or vertigo during their routine AE monitoring queries will rate the severity of the dizziness using the DHI. The self-administered questionnaire takes 5-10 minutes to complete and doesn't require special training to administer. Respondents choose the statement that most describes them. The statements are scored from 0 – 4 and scores can range from 0 – 100 ([Whitney 2004](#)). The questionnaire will be self-administered and scored by the designated study personnel. The DHI has been validated and can detect statistically significant change over time in group data ([Enloe 1997](#)).

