9.2.10. Columbia-Suicide Severity Rating Scale (C-SSRS)

The C-SSRS is a 2-page form ([Appendix 7](#)) asking questions about suicidal ideation, intensity of ideation, and suicidal behavior developed by Posner and collaborators at the New York State Psychiatric Institute ([Oquendo-2003](#)). This scale is intended for use by trained administrators. The questions contained in the C-SSRS are suggested probes. Ultimately, the determination of the presence of suicidality depends on clinical judgment. Training is required before administering the C-SSRS through a 30-minute interactive slide presentation followed by a question-answer session through the Columbia Lighthouse Project. Those completing the training are certified to administer the C-SSRS, and will receive a training certificate. As the MINI will be used to establish subject initial eligibility with respect to suicidality, the "Since Last Visit" version of the C-SSRS interview will be conducted at the randomization visit prior to the first dose and then every 4 weeks \pm 1 week thereafter through Week 64. The interview can be conducted by telephone at all scheduled times or in person at the clinic visit. At Week 1, this scale will be used to assess current suicidal ideation since the MINI interview. This questionnaire will be administered by a clinical staff member and subject responses will be recorded either on a paper CRF or electronically into an eCRF. If an eCRF is used, it will serve as both the source and eCRF.

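### AE and concomitant-medication questions are scheduled only at clinic visits, so the longest recall interval (28 weeks) falls on the beyond-6-month period the trial is meant to study, although staff already contact every participant every 4 weeks

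*Combined protocol and SAP*

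**What the plan says.** Section 5.6 gives the reason for 12 months of dosing: "to confirm the long term safety of tafenoquine past the 6-month safety window for travelers or military personnel". Section 5.2.2 makes the incidence, severity and relationship of AEs a secondary endpoint, along with dizziness or vertigo and its severity on the DHI. Section 12.2.3.2 tabulates AEs at the 1% and 10% levels.

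The schedule in Section 1 marks AE and concomitant-medication collection at Week 1 Day 1 and Weeks 4, 12, 24, 52 and 64. Section 8.3 lists "Recording AEs and any concomitant medications" among the assessments at the treatment-period visits. Section 6.4.2 says: "All participants will be questioned about concomitant medication at each clinic visit". The Week 24 visit has a window of 2 weeks either side, and so does the last on-treatment visit ("Week 52 ± 2 weeks").

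Section 8.3 also says that every 4 weeks, within 1 week either side, "a C-SSRS interview will be conducted either by telephone at any time or in person at a clinic visit". Section 8.4 continues this to Week 64. Section 9.2.10 describes the instrument as "asking questions about suicidal ideation, intensity of ideation, and suicidal behavior".

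On dizziness, Section 9.2.9 says: "Participants who admit to new or worsening dizziness or vertigo during their routine AE monitoring queries will rate the severity".

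**The concern.** A trial extended to 12 months to learn what happens after month 6 asks about AEs least often after month 6. From Week 24 to Week 52 the plan relies on participants volunteering events, or remembering them at Week 52.

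Mild, short-lived events are the ones most easily lost over months: a spell of dizziness, poor sleep, abnormal dreams, a gastrointestinal upset. Those that are remembered will have less reliable onset and stop dates, severity ratings and records of medication taken. At stake are the AE tables, the dizziness and DHI endpoint, and any reading of AE rates before and after 6 months. With 300 per arm the 1% level is 3 participants, so one forgotten case takes a term from 3/300 (1.0%) to 2/300 (0.7%) and below that level.

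**Working it through.** The plan gives no figure of its own for this point. The calculations in Section 12.1 concern the imaging-based SOSE rate and are not in question here.

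**1. Intervals between scheduled AE questions.** Query weeks (Section 1): 1, 4, 12, 24, 52, 64.

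- Differences: 3, 8, 12, 28 and 12 weeks.
- Range of the 28-week interval within windows: 28 − 4 = 24 to 28 + 4 = 32 weeks.
- Longest interval before Week 24: 12 weeks nominally.
- At nominal visit times, all dosing from Week 26 to Week 52 lies inside the 28-week interval and is covered by one scheduled question, at Week 52.

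**2. Density of questions.**

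- Weeks 1 to 24: 3 questions in 23 weeks = 0.130 per week.
- Weeks 24 to 52: 1 question in 28 weeks = 0.036 per week.
- Ratio: 0.130 / 0.036 = 3.7.

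**3. Mean wait from event to next question.** With events arising at a constant rate, the mean wait is Σ(gap²) / (2 × Σ gap).

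- Weeks 1 to 24: (9 + 64 + 144) / (2 × 23) = 217 / 46 = 4.7 weeks.
- Weeks 24 to 52: 784 / 56 = 14 weeks.
- With a question every 4 weeks: 16 / 8 = 2 weeks.

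**4. Does another instrument fill the gap?**

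- Diary card (Section 7.5.1): doses taken.
- Text-message system (Sections 7.3.1 and 7.3.2): date, time and number of tablets, plus reminders.
- C-SSRS contact (Section 9.2.10): suicidality only.
- M.I.N.I. and LSEQ (Section 1): at clinic visits, so they share the gap.
- DHI: only after a report of dizziness or vertigo.

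None contains a general AE question.

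**5. Contacts already in place.** Every 4 weeks from Week 24 gives nominal contacts at Weeks 28, 32, 36, 40, 44 and 48: six. Over Weeks 4 to 64 there are 16 four-weekly contacts, of which 5 coincide with visits (Weeks 4, 12, 24, 52 and 64), leaving 11.

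**6. Effect on comparisons.** If a fraction q of events is lost in both arms, rates p1 and p2 are seen as (1 − q)p1 and (1 − q)p2. The absolute difference shrinks to (1 − q)(p1 − p2). The risk ratio is unchanged, and the odds ratio is nearly so for uncommon events.

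**7. Size of q.** The documents do not give it. As an assumption only, take events that would never be volunteered, and let recall decay exponentially with time constant τ. The share captured over an interval L is (τ/L)(1 − e^(−L/τ)).

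| τ (weeks) | Weeks 1–24, as planned | Weeks 24–52, as planned | Weeks 24–52, asked every 4 weeks |
|---|---|---|---|
| 8 | 60% | 28% | 79% |
| 13 | 72% | 41% | 86% |
| 26 | 84% | 61% | 93% |
| 52 | 92% | 77% | 96% |

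The range is wide and applies only to events that depend on being asked. The ordering is the same throughout: capture is lowest in the second half, and the 4-weekly question lifts it above the first-half level.

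**The case against.** The strongest reply is that capture between visits is not zero. Section 10.11.2 has the investigator record all AEs continuously from Day 1 to Week 64, including spontaneous reports, so an event mentioned on a C-SSRS call would have to be recorded. Section 8.7 provides for unscheduled visits. The general text closing Section 8.5 has participants reminded at all follow-up visits to contact the site about AEs and new medication, and Section 5.1 uses that term for the treatment-period visits as well. AE procedures are also partly delegated to a Study Safety plan that is not among these documents. All of this stands, and it limits the size of the problem. It does not replace active questioning, which Section 10.11.2 itself names as a source of AEs and which is not scheduled for 28 weeks.

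Several stronger readings are tempting but unsupported:

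- A reader might infer that most of the treatment period goes unasked about. The Week 52 question covers those weeks; what is long is the recall interval.
- A reader might infer that emerging harms generally reach the investigator and the DSMB only after the whole interval. Sections 10.2 and 10.11.5 require SAEs and AESIs to be reported within 24 hours of awareness, and the DSMB meets quarterly (Section 10.9). The delay concerns non-serious events that the participant does not volunteer.
- A reader might infer that dizziness in Week 28 cannot be rated until Week 52. The DHI is triggered by the event, so a volunteered report could be rated at an unscheduled visit. Only an unvolunteered one would wait.
- A reader might infer bias between arms. The schedule is the same in both blinded arms, and no formal comparison of the two halves of treatment is planned; summaries by visit are descriptive.

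**Conclusion.** The point holds as a weakness in active AE ascertainment that should be corrected. The 28-week interval (24 to 32 within windows), its position over the period beyond 6 months, the 3.7-fold lower question density and the six available contacts follow from the schedule alone. The mean waits of 4.7 and 14 weeks assume a constant event rate.

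The likely consequence is that mild, transient, non-serious AEs are under-counted and poorly dated in both arms. Absolute differences are then attenuated, and rates before and after 6 months become less comparable. How many events would be lost cannot be derived from the documents, so no specific loss should be quoted as a finding.

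The primary SOSE endpoint rests on imaging and does not depend on recall. Laboratory- and test-based AESIs and most SAEs are also little affected.

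**What to change.** In Section 1 and Sections 8.3 and 8.4, add to each 4-weekly C-SSRS contact the same open, non-leading AE question that is used at visits, with a concomitant-medication update. Apply it identically in both arms and record the mode of collection (telephone or in person) in the eCRF. Align Section 6.4.2, which ties medication questioning to clinic visits. If dizziness or vertigo is reported, have the participant complete the DHI at that time, for example on a copy held at home or sent electronically. This keeps the self-administered format in Section 9.2.9; reading the DHI out by telephone would depart from it.

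The longest interval then falls from 28 weeks to 4 (about 6 when the 1-week windows fall at opposite ends), and the mean wait in Weeks 24 to 52 from 14 weeks to 2.

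No new visits or procedures are needed. The cost is a few minutes on calls that already take place, a schedule row and an eCRF page: up to 11 × 600 = 6,600 additional queries if all participants stay to Week 64. More minor AEs will also need assessment by a medically qualified investigator (Section 10.2) and full source verification (Section 11.2). The documents do not show whether existing staff can absorb this.

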8.4. Early Termination/EOS assessments, Weeks 64 (Visit 7a and 7b)

This visit scheduled to occur during Study Week 64, will be conducted over two days during this week to complete all assessments. Data will be recorded at the nominal Week 64 visit.

Due to the long $t_{1/2}$ of tafenoquine (13-15 days with an expected 65-75-day washout period), all participants will return to the clinic at Week 64 for their EOS visit. If a participant withdraws prematurely; all these study checks should be completed at the final outgoing visit, preferably 65-75 days after their last dose of IMP:

- Full physical examination;
- Vital signs (blood pressure, pulse rate, respiratory rate and sublingual body temperature);
- 12-lead ECG;
- Blood sampling for determination of the following parameters:
 - CBC and biochemistry;
 - MetHb %;
 - Serum β -HCG pregnancy test (WOCBP only);

- Urine sampling for determination of the following parameters:
 - Urinalysis (dipstick and urine microscopy if blood, leukocyte esterase, or nitrites are positive); and,
- **Ophthalmic Assessments:**
 - Before pupil dilation:**
 - BCVA (ETDRS letter score);
 - Color vision assessment with FM-100 hue test;
 - Mars letter contrast sensitivity test;
 - M-chart distortion test; and
 - Slit lamp examination;
 - After pupil dilation:**
 - MAIA microperimetry;
 - Heidelberg Spectralis SD-OCT (including wide field macula scan);
 - Heidelberg Spectralis qFAF (set of 3 images to ensure consistency in measurement);
 - Digital photograph of corneal surface (conventional and wide field);
 - Digital photograph of retina (conventional and wide field);
 - Slit lamp retinal examination and IOP measurement
- **Psychiatric Assessments**
 - M.I.N.I. English Version 7.0.2;
 - DHI (only if a participant reports AE of dizziness or vertigo); and
 - LSEQ.
- Recording AEs and any concomitant medications.

Also every 4 weeks \pm 1 week between the Week 52 and the Week 64 visit, a C-SSRS interview will be conducted.

8.5. Part 3 Follow-up for Ongoing AEs Weeks 76, 89, and 104 (Visits 8, 9, and 10):

The following are the criteria for participant continuation for additional safety assessments:

- Ongoing AE.
- Laboratory value is determined to be a new or continuation of an ongoing AE.
- Diagnosis of psychiatric disorder.
- Abnormality found on any of the following ophthalmologic examinations (only the test that revealed an abnormality will be repeated, unless at the discretion of the investigator additional testing is warranted):

- SD-OCT, qFAF, BCVA [ETDRS], FM-100 hue test, Mars letter contrast sensitivity test and M-chart.
- Slit lamp examination and digital photograph of corneal surface (cornea Verticillata) and retinal digital photograph (toxic maculopathy and retinopathy on conventional and wide field device).
- Microperimetry.

Participants will report to the Study Site in the morning.

The following assessments will be performed during this follow-up visit (if required):

- Blood sampling as needed to follow abnormality:
 - CBC and biochemistry;
 - MethHb %;
- Urine sampling as needed to follow abnormality:
 - Urinalysis (dipstick and urine microscopy if blood, leukocyte esterase, or nitrites are positive).
- Ophthalmic Assessments (repeat only if abnormal at Week 64). Abnormal results may need to be further investigated using microperimetry, color vision assessment with FM-100 hue test, Mars letter contrast sensitivity test and M-chart. Corneal deposits and retinal lesions from drug toxicity at Week 64 needed to be monitored by slit lamp examination, SD-OCT (including wide field macula scan), qFAF and photography (conventional and wide field);
- Psychiatric Assessment with M.I.N.I 7.0.2 (repeat if disorders are found at Week 64).
- Assessment with DHI (if participant reports ongoing AE of dizziness or vertigo).

General:

At all follow-up visits, participants will be reminded of the following before leaving the Study Site:

- Study restrictions as described in [Section 6.4](#);
- To return to the Study Site for the following scheduled visit; and
- To contact the Study Site in the interim should they experience AEs or require treatment with any concomitant medications.

